9. RESEARCH METHODS

9.1. Study design

This is a retrospective, observational study using January 1, 2006 – December 31, 2023 data from the National VA Health Care Network databases. PC patients who initiated relugolix will be selected based on diagnosis codes, age, treatment received, and continuous activity in the health care network. The identification period for relugolix use will be from December 18, 2020 to December 31, 2023. December 18, 2020 is the approval date for relugolix in the US, and December 31, 2023 is the end of available data. The index date will be defined as the initiation date of relugolix. The baseline period will be 365 days prior to the index date (hence the start of the study period is December 18, 2019). The follow-up period will be from the index date to the earliest of death, end of continuous eligibility or end of data availability. Most of the patient characteristics will be described during the baseline period. Certain patient characteristics will be described using all data available prior to the index date (i.e., data prior to December 18, 2019 will also be used if available; see more details in Table 2). Treatment patterns, adherence, and persistence with relugolix, and PSA and testosterone responses (if sample size allows) will be assessed during the follow-up period.

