Index treatment	
Index treatment regimens include:
 
 • Relugolix monotherapy • Relugolix + NSAA only (at least 90 days of NSAA use) • Relugolix + ARPI +/- NSAA (no chemotherapy) • Relugolix + ARPI + chemotherapy • Relugolix + chemotherapy +/- NSAA (no ARPI) • Relugolix + other (no ARPI, no chemotherapy) 
Index treatment regimen will be defined based on treatments received within 30 days before the index date and within 90 days after the index date.
 
Specific treatments included in each treatment category (i.e., ADT, NSAA, ARPI, chemotherapy, immunotherapy) are described in “Treatment history” in Table 2. Other treatments include immunotherapy, radium 223, olaparib, rucaparib, talazoparib, niraparib and lutetium Lu 177 vipivotide tetraxetan.
 
Number of patients who received any radiotherapy during the index treatment will be summarized.

Variable	Operational definition
Treatment patterns of relugolix	
Treatment patterns of relugolix include:
 
• Continued relugolix as in the index treatment (regardless of discontinuation of concomitant medications)• Continued relugolix with a new add-on systemic PC treatment (excluding ADT)• Discontinued relugolix and switched to another ADT treatment• Discontinued relugolix without switching to another ADT treatment 
Add-on systemic PC treatments include:
 
• ARPI• NSAA• Chemotherapy• Immunotherapy• Radium 223• Ketoconazole• Olaparib• Rucaparib• Talazoparib• Niraparib• Lutetium Lu 177 vipivotide tetraxetan 
Add-on therapy will be evaluated from 90 days after the index period to the end of the follow-up period.

Time to treatment changes	The time to treatment changes of interest include: 
• Time to discontinuation of relugolix• Time to switching to a different ADT treatment• Time to add a new systemic PC treatment to relugolix
Treatment adherence	Adherence to relugolix post the index date will be described using both MPR and PDC: 
• MPR: Sum of the days of supply divided by the number of days between the first fill and the end of the last refill (i.e., including the days of supply from the last refill)• PDC: Sum of the non-overlapping (i.e., not double counting of overlaps) days of supply covered

Variable	Operational definition

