	divided by a pre-determined period following treatment initiation (e.g., 6 and 12 months) Adherence will be described as a continuous variable and as a binary variable (<0.80: non-adherent, ≥ 0.80 : adherent)
Treatment persistence	Persistence to relugolix will be described as the proportion of patients who did not discontinue relugolix (i.e., with a treatment gap, switch to another ADT, or death; the minimum days of treatment gap, e.g., 45 or 60 days, will be finalized based on sample size and clinical input) during the follow-up period. Treatment gaps will be assessed from the end of the days of supply of the previous prescription to the earliest of the next prescription or the end of data availability.
PSA response	Only if sample size is sufficient and among patients with at least one baseline and one follow-up period PSA measure: 
• The number and percentage of patients with $\geq 50\%$ and $\geq 90\%$ decline from the baseline PSA to any PSA measurement during the follow-up period and while on relugolix• The number and percentage of patients with the nadir PSA value during the follow-up period and on treatment of relugolix < 0.01, 0.1, and 0.2 ng/mL
Testosterone response	Only if sample size is sufficient and among patients with at least one follow-up period testosterone measure: 
• The number and percentage of patients with at least one testosterone value of <50ng/dL and <20 ng/dL during the follow-up period and while on relugolix 
If sample size is sufficient, the analysis above may be conducted among patients with at least one baseline and one follow-up period testosterone measure

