The same descriptive analysis described in [Section 9.7.1](#) will be conducted in Black and non-Hispanic White patients separately. If the sample sizes allow, SMD will be calculated to compare the patient baseline characteristics between Black vs. non-Hispanic White cohorts. Additionally, p-values from appropriate statistical tests (e.g., t-tests or rank-sum tests for continuous variables and chi-square tests for categorical variables) comparing Black vs. non-Hispanic White cohorts will be reported.

9.7.6. Data analysis for Objective 6: To describe and compare time to treatment changes between Black and non-Hispanic White patients with PC who initiated relugolix

The same descriptive analyses described in Section 9.7.2.3 will be conducted in Black and non-Hispanic White patients separately. Unadjusted and adjusted comparisons between the two race groups will be conducted. Cox proportional hazards (PH) regressions will be used to compare the time to treatment changes between the two race groups. Patient characteristics to be included in the adjusted models will be selected based on findings in Section 9.7.5 and clinical input.

9.7.7. Data analysis for Objective 7: To estimate and compare adherence and persistence with relugolix between Black and non-Hispanic White patients with PC who initiated relugolix

The same descriptive analyses described in Section 9.7.3 will be conducted in Black and non-Hispanic White patients separately. Unadjusted and adjusted comparisons between the two race groups will be conducted. Generalized linear models will be used to compare adherence to relugolix between the two race groups. Cox PH regressions will be used to compare persistence between the two race groups. Patient characteristics to be included in the adjusted models will be selected based on findings in Section 9.7.5 and clinical input.

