9.9. Limitations of the research methods

The analyses conducted as part of this study are subject to the following limitations, which will be addressed in any write-up of the study:

- As this study will be conducted among veterans, its findings may not be generalizable to other populations
- Certain assumptions will be made in order to depict treatment patterns. However, the definition of treatment patterns will nevertheless be subject to assumptions that may not match up to the prescribing physicians' intent
- Data are subject to inaccuracies in coding of diagnoses. The presence of a diagnosis code in the data does not necessarily mean the presence of disease. The disease may be incorrectly coded, or the code was included as a rule-out criterion
- The presence of a prescription does not necessarily mean the medication was consumed as prescribed. In addition, prescriptions filled over the counter or provided as samples by the physician are not included in the data

- The fact that our entry criteria is at least 2 subscriptions of relugolix means we are selecting patients who were able to tolerate the first month and followed up to receive a second month. How this cohort relates to all patients given relugolix is unknown.

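### Read literally, the persistence gap rule carries no leftover supply forward, so a measured gap is the real gap plus any stock in hand; build one supply timeline for both gaps and PDC

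*Combined protocol and SAP*

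**What the plan says.** Table 3 counts a man as having discontinued relugolix on a treatment gap, a switch to another ADT, or death. The gap is timed as follows: "Treatment gaps will be assessed from the end of the days of supply of the previous prescription to the earliest of the next prescription", or to the end of data availability if there is no further fill. Its minimum length is open: "the minimum days of treatment gap, e.g., 45 or 60 days, will be finalized based on sample size and clinical input".

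The same table has two adherence measures that also handle overlapping fills. One is "MPR: Sum of the days of supply divided by the number of days between the first fill and the end of the last refill", which credits all dispensed supply. The other is "PDC: Sum of the non-overlapping (i.e., not double counting of overlaps) days of supply covered", divided by a fixed window. The PDC wording rules out counting a day twice. It does not say whether the overlapping days are moved to the end of the existing supply or dropped.

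No section states a carry-forward rule for gaps, and Annex 1 lists no stand-alone document that could hold one. The definition feeds the treatment patterns and time to discontinuation (Section 9.7.2), the persistence curve (Section 9.7.3) and the Cox comparisons by race (Sections 9.7.6 and 9.7.7).

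**The concern.** A man who refills before he runs out holds tablets from earlier fills. If the clock starts when the latest fill's own supply would have ended, those tablets are invisible to the gap rule. His apparent gap is longer than his time without drug, by exactly the stock he held when he collected that fill. Two things can follow. A short interruption, or none, can reach the minimum gap and be counted as discontinuation. And if the event is dated at the start of the gap, a man who truly stops with stock in hand is dated too early.

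The inflation reflects refill habit and fill length, not stopping. The overlap that can produce a gap here is credited in full by MPR, so one man can be adherent on MPR and discontinued on persistence. Two competent programmers could also derive different discontinuation dates from the same fills.

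**Working it through.** **Inputs.** The gap rule, MPR and PDC come from Table 3, as do the example minimum gaps of 45 and 60 days. Fill length is not stated; Section 9.9 hints at roughly monthly fills ("we are selecting patients who were able to tolerate the first month and followed up to receive a second month"). The fill lengths of 30 and 90 days and all fill dates below are therefore assumptions. The plan gives no figure to reproduce.

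**Formulas.** Let fill *k* be on day t(k) with d(k) days of supply.

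- Gap as written = t(k+1) − [t(k) + d(k)].
- Run-out with carry-forward: R(k) = max[R(k−1), t(k)] + d(k). Gap = t(k+1) − R(k), or 0 if negative.
- Stock held at fill *k*: S = R(k) − [t(k) + d(k)]. If the next fill comes at or after run-out, gap as written = real gap + S. A minimum gap *m* then acts as *m* − S.

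**Example 1: 30-day fills on days 0, 25, 50, 75, 100, 125 and 205.**

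- As written: 205 − (125 + 30) = 50 days.
- Carry-forward: run-out at 6 × 30 = day 180, gap 205 − 180 = 25 days, so S = 25.
- At a 45-day minimum he is discontinued as written and persistent with carry-forward. At 60 days he is persistent both ways.
- MPR = 210/235 = 0.89, adherent.
- If he never refilled, the gap would start on day 155 as written and on day 180 with carry-forward, 25 days apart whatever the minimum.

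**Example 2: 90-day fills on days 0, 75, 150, 225 and 360 (never without drug).**

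- As written: 360 − (225 + 90) = 45 days.
- Carry-forward: run-out at 4 × 90 = day 360, gap 0.
- Discontinued as written at a 45-day minimum, not at 60.
- MPR = 450/450 = 1.00. Twelve-month PDC is (315 + 5)/365 = 0.88 if overlaps are dropped and 1.00 if shifted.

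**Example 3: a 90-day fill on day 0, a 30-day fill on day 10, the next fill on day 95.**

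- As written: 95 − (10 + 30) = 55 days, although the first fill alone covers him to day 90. PDC counts days 40 to 90 as covered on either reading.
- Carry-forward: run-out at 90 + 30 = day 120, gap 0.
- Discontinued as written at 45, not at 60.

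**How much stock is needed.** A man who never runs out can be misclassified only if his stock reaches the minimum gap. That takes at least ⌈m / days early⌉ early refills:

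| Days early each time | m = 45 | m = 60 |
|---|---|---|
| 5 | 9 | 12 |
| 7 | 7 | 9 |
| 10 | 5 | 6 |
| 15 | 3 | 4 |

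He must then leave a long interval while he uses that stock up.

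**Simulation under assumed refill timing.** Men who never run out refill with a uniform 0 to X days in hand (4,000 men per setting). The share misclassified:

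| X (days) | m (days) | 30-day fills, 1 / 2 years | 90-day fills, 1 / 2 years |
|---|---|---|---|
| 45 or less | 45 or 60 | 0% / 0% | 0% / 0% |
| 60 | 45 | 19% / 38% | 9% / 21% |
| 60 | 60 | 0% / 0% | 0% / 0% |
| 90 | 60 | 23% / 45% | 17% / 34% |

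This covers only men with no real gap. It does not count men like the one in Example 1, whose modest stock adds to a short real gap.

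**The case against.** The best reply is that Table 3 is silent rather than wrong. The end of the days of supply could be programmed as a stock-adjusted run-out date, and the PDC wording fits shifting overlaps forward as well as dropping them. That is fair as far as it goes. The MPR/PDC conflict in particular appears only if overlaps are dropped. But the gap wording points to one prescription's supply, and no text supplies the other reading, so the rule still has to be stated.

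The second reply is that the minimum gap absorbs ordinary early refilling. This largely stands for men who never run out: with up to 45 days in hand, none was misclassified at either minimum, and all three examples are persistent at 60 days. It does not cover stock added to a short real gap, or the dating of true discontinuations.

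Third, the affected objectives are exploratory, no hypotheses are prespecified (Section 9.5), and Section 9.9 already says treatment patterns rest on assumptions. That limits the weight of the point but does not remove it.

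A reader might infer that continuously supplied men will generally be counted as discontinued, or that the race hazard ratios are distorted. The documents support neither. The first needs stock of at least the minimum gap followed by a long refill interval. The second needs refill timing or fill length to differ by race, and nothing in the protocol says that they do.

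**Conclusion.** The point holds as a cheap improvement to an incompletely specified rule. Followed literally, Table 3 measures the real gap plus stock in hand and can therefore create false discontinuations. If events are dated at the start of the gap, which neither Table 3 nor Section 9.7.2.3 states, true discontinuations with stock in hand are dated early by the size of that stock.

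The individual errors are exact (50 days against 25 in Example 1), but the number of men affected is unknown. It depends on fill length, refill timing and a minimum gap still to be finalized. The consequences are confined to Objectives 2, 3, 6 and 7; the primary description of baseline characteristics is untouched. Any effect on the race comparison is conditional on refill patterns differing between the groups.

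**What to change.** In Table 3, define one relugolix supply timeline per patient. A fill dispensed before earlier supply runs out starts when that supply ends. Measure treatment gaps from the end of the accumulated supply, and count PDC covered days from the same timeline, capped at the end of the window. Report the version without carry-forward as a sensitivity analysis.

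The cost is one or two sentences and a standard programming step. The downside is small: a fill that replaces lost tablets would slightly overstate coverage, and the sensitivity analysis would show how much the choice matters.

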9.2.1. Inclusion criteria

Patients who met all of the following sample selection criteria will be included:

- Male with ≥ 1 diagnosis of PC (International Classification of Diseases, 10th Revision, Clinical Modification [ICD-10-CM] C61)
- Had ≥ 2 prescriptions of relugolix on or after the first observed PC diagnosis. The initiation date of relugolix will be selected as the **index date**
- At least ≥ 18 years old as of the index date
- Had continuous activity in the data for ≥ 365 days prior to the index date and ≥ 90 days since the index date (unless died within 90 days). The **baseline period** will be defined as the 365-day period prior to the index date. The **follow-up period** will be from the index date to the end of continuous eligibility, data availability, or death, whichever happened first

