9.3. Variables

Baseline variables (Table 2) will be measured during the baseline period (365 days prior to the index date). Treatment patterns, adherence and persistence, and clinical variables (Table 3) will be measured during the follow-up period.

Table 2. Baseline demographic and clinical characteristic variables

Variable	Operational definition
Age	Age will be defined as of the index date and retained in the dataset as a continuous variable and a categorical variable (e.g., ≤ 59 , 60-69, 70-79, ≥ 80 years old).
Race/ethnicity	Proportion of patients that were non-Hispanic White, Black, Hispanic, other or unknown will be summarized.
Geographic regions	Proportion of patients that lived in Northeast, Midwest, South and West areas will be summarized.
Index year	A categorical variable for the index calendar year will be summarized.
Site of metastasis	Proportion of patients that had a metastatic diagnosis at the following sites: bone only, bone and node only, node

PFIZER CONFIDENTIAL

Variable	Operational definition
	only, viscera and other, will be summarized among patients with metastatic PC. All data available prior to the index date will be used.
Treatment history	
Proportion of patients who had each of the following treatments in the baseline period will be evaluated:
 
• Prostatectomy• Chronic oral corticosteroid use• Pain medication (opioids)• ADT treatment (leuprolide, degarelix, goserelin, histrelin, triptorelin)• Androgen receptor pathway inhibitor (ARPI; abiraterone, apalutamide, darolutamide, enzalutamide)• Non-steroidal anti-androgen (NSAA; bicalutamide, nilutamide, flutamide)• Chemotherapy (docetaxel, cabazitaxel, carboplatin, oxaliplatin, cisplatin, mitoxantrone)• Immunotherapy (sipuleucel-T, pembrolizumab)• Radium 223• Systemic ketoconazole• Olaparib• Rucaparib• Talazoparib• Niraparib• Lutetium Lu 177 vipivotide tetraxetan• Radiotherapy 
Treatments considered as a part of index treatment regimen will not be flagged as baseline treatments if received within 30 days prior to index date.

Time from first observed PC diagnosis date to the index date	Time from the first observed PC date in the data to the index date will be evaluated. All data available prior to the index date will be used.
NCI Charlson Comorbidity Index (CCI) score	The NCI version of the CCI score will be created during the baseline period.

Variable	Operational definition

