Comorbidities	A binary variable (yes/no) will be created for patients with a diagnosis of each of the following comorbidities during the baseline period: 
• Hypertension• Hyperlipidemia• Diabetes• Urinary tract infection• Chronic obstructive pulmonary disease• Arrhythmia• Congestive heart failure• Myocardial infarction• Stroke• Angina pectoris• Inflammatory bowel disease• Acute coronary syndrome• Sexual dysfunction• Depression• Anxiety• Hot flashes• Cognitive impairment• Major adverse cardiovascula event (defined by any evidence of cardiomyopathy, heart failure, ischemic heart disease, myocardial infarction, pulmonary embolism, or stroke)
PSA	Baseline PSA value (among available) based on the PSA value closest to the index date during the 90-day window (or 180-day, to be finalized based on the number of patients with non-missing PSA value in these time frames) on or prior to the index date will be evaluated.
Testosterone	Baseline testosterone value (among available) based on testosterone value closest to the index date during the 90-day window (or 180-day; will be consistent with the time window for baseline PSA) on or prior to the index date will be evaluated.
Metastatic vs. non-metastatic PC	A binary variable for patients with metastatic vs. non-metastatic PC will be created. Metastatic PC will be

Variable	Operational definition
	defined as having evidence of metastasis during the baseline period or within 90 days since the index date.
ADT naïve vs. ADT experienced	A binary variable for patients who were ADT naïve vs. ADT experienced will be created. ADT naïve will be defined as having no records of any systemic ADT treatment ever based on all available data prior to the index date (i.e., including baseline period data and any available data prior to the baseline period). Systemic ADT treatment includes LHRH agonists and GnRH antagonists (i.e., degarelix, relugolix, goserelin, histrelin, leuprolide, triptorelin)

Table 3. Treatment patterns, adherence, persistence, and clinical variables during the follow-up period

Variable	Operational definition

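### Table 3 runs treatment gaps past the end of follow-up, so some patients who leave the VA can be counted as having stopped relugolix

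*Combined protocol and SAP*

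**What the plan says.** Section 9.1 fixes the end of observation: "The follow-up period will be from the index date to the earliest of death, end of continuous eligibility or end of data availability". Section 9.2.1 agrees; its follow-up period "will be from the index date to the end of continuous eligibility, data availability, or death, whichever happened first".

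Several places put persistence inside that period. Section 9.1: "Treatment patterns, adherence, and persistence with relugolix, and PSA and testosterone responses (if sample size allows) will be assessed during the follow-up period". Section 9.3: "Treatment patterns, adherence and persistence, and clinical variables (Table 3) will be measured during the follow-up period". The table title: "Table 3. Treatment patterns, adherence, persistence, and clinical variables during the follow-up period". The Treatment persistence row of Table 3 also places discontinuation within follow-up. It counts a treatment gap, a switch to another ADT or death as discontinuation, and gives 45 or 60 days as examples of the minimum gap.

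The next sentence of that row runs the gap from the end of the previous supply "to the earliest of the next prescription or the end of data availability". End of eligibility is not listed.

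Sections 9.7.2.3 and 9.7.3 specify Kaplan-Meier analysis, and Sections 9.7.6 and 9.7.7 add Cox models. None says who is censored, when, or on which day a gap-based discontinuation is dated. The complete-follow-up requirement in Section 9.7.3 applies to adherence only. Section 9.2.1 selects patients by activity ("Had continuous activity in the data for" at least 365 days before and 90 days after index) and then ends follow-up by eligibility. It says how neither is measured. Annex 1 lists no stand-alone document that might.

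**The concern.** Once a patient leaves the VA, the data hold no further fills, whether or not he still takes the drug. If the gap keeps running to 31 December 2023, the absence of records becomes evidence of stopping. The persistence curve (Objective 3), time to discontinuation (Objective 2) and the race comparisons (Objectives 6 and 7) could then mix stopping relugolix with leaving the health system.

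The Table 3 pattern counts are exposed too, notably "Discontinued relugolix without switching to another ADT treatment", if they use the persistence row's definition of discontinuation; no other is given. The primary objective describes baseline characteristics and is not affected.

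**Working it through.** **Two patients, two answers.** Suppose supply ends on day 190, eligibility on day 200 and data on day 600, with no further fill. By the Table 3 sentence the gap is 600 − 190 = 410 days, which exceeds 45 or 60, so he has discontinued. By the follow-up definition the observable gap is 200 − 190 = 10 days, so he is censored on day 200. Confining persistence to follow-up does not remove the event if it is dated at end of supply, because day 190 lies inside follow-up. Now swap the two dates, so that he leaves on day 190 with supply to day 200. The literal gap is 600 − 200 = 400 days, an event, although he left with drug in hand.

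**Three rules for a gap-based event.**
- Aligned: end of supply + minimum gap ≤ end of follow-up.
- Narrow: end of supply ≤ end of eligibility, and end of supply + minimum gap ≤ end of data.
- Literal: end of supply + minimum gap ≤ end of data. This spares only patients whose supply ends within one gap length of 31 December 2023.

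**Inputs.** From the documents: identification from 18 December 2020, data to 31 December 2023, 90 days after index (so the last index date is 2 October 2023), at least two fills, and a gap of 45 or 60 days. Assumed: true 12-month persistence of 65%; leaving at 2%, 5% or 10% per year after day 90; 30-day fills 2 or 4 days late, or 90-day fills 2 days late; 60% or 100% of stopping gap-based, the rest switch or death. Each setting used 250,000 to 300,000 simulated patients. The plan states no persistence rate, so it has no figure to reproduce.

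**12-month persistence (%).** Example: 30-day fills 2 days late, 60-day gap, all stopping gap-based, event on the day the threshold is reached.

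| Yearly leaving | True | Aligned | Narrow | Literal | Aligned − narrow | Aligned − literal |
|---|---|---|---|---|---|---|
| 2% | 64.9 | 65.0 | 64.9 | 64.2 | 0.1 | 0.8 |
| 5% | 64.9 | 64.9 | 64.6 | 63.1 | 0.3 | 1.8 |
| 10% | 64.7 | 64.7 | 64.1 | 61.1 | 0.6 | 3.6 |

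Over all settings at 65%, the narrow rule is lower than the aligned rule by 0.1–0.2, 0.1–0.5 and 0.2–1.0 points at 2%, 5% and 10% leaving. The literal rule is lower by 0.6–1.0, 1.6–2.5 and 3.4–5.0 points (0.5–1.2, 1.2–2.9 and 2.6–5.8 if true persistence is 50% to 80%).

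A second, simpler simulation (true persistence 75%, 60-day gap) gave literal shortfalls of 76.6 − 75.5 = 1.1, 76.9 − 73.9 = 3.0 and 77.0 − 71.2 = 5.8 points. It supports the direction and order of size. It does not show which rule is nearer the truth, because it dated events at end of supply while counting patients on drug to end of follow-up, which lifts the curve.

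**Pattern counts.** The extra share of the cohort classed as stopped without a switch, at 2%, 5% and 10% leaving, is 0.1–0.3, 0.2–0.8 and 0.5–1.6 points (narrow), or 1.5–1.7, 3.6–4.2 and 7.4–8.4 points (literal).

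**Race hazard ratio, equal true stopping.** With equal leaving it is 0.996–1.006. With leaving of 3% v 2%, the literal rule gives 1.01–1.02; with 5% v 3%, 1.02–1.03. The narrow rule gives 1.00–1.01, within simulation noise of about 0.005–0.01.

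**When stoppers also vanish.** Suppose eligibility ends at last recorded activity and some gap-based stoppers have none afterwards. At 5% leaving with threshold-day dating, 12-month persistence (%) is:

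| Stoppers lost | Aligned, all gap-based | Aligned, 60% gap-based |
|---|---|---|
| 0% | 65.0 | 64.9 |
| 5% | 66.3 | 65.6 |
| 10% | 67.6 | 66.4 |
| 20% | 70.5 | 67.9 |

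The literal rule stays at 63.2 and 63.1. In a separate run with all stopping gap-based, the narrow rule stayed at 64.4–64.6 against a true 64.8–64.9. Across settings, the aligned rule overstated persistence by 0.7–1.4, 1.5–2.8 and 3.0–5.8 points at 5%, 10% and 20% lost.

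**The case against.** **The literal reading takes one sentence alone.** A reader might infer that the plan counts everyone who leaves on drug as discontinued and so understates persistence by up to 5 points. The documents do not support that as the intended rule. The sentence just before it, the table title and Sections 9.1 and 9.3 confine persistence to follow-up, and a gap that opens after follow-up has ended is not a discontinuation within it. This stands, and it makes the narrow reading the better one. If discontinuation were also dated on the threshold day and had to fall within follow-up, the conflict would vanish. The plan gives no date, so that cannot be assumed.

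**Censoring at end of follow-up is ordinary Kaplan-Meier practice.** That is true for event-free patients. It does not say whether the patient with supply to day 190 and eligibility to day 200 is event-free.

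**The aligned rule is not uniformly better.** This stands. If 20% of stoppers leave no later record, it errs further than the literal rule does. Running gaps to end of data could be a defensible choice, but the plan does not present it as one.

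**The undated event is a separate matter.** It is. Using the threshold day instead of end of supply raises 12-month persistence by 0.65^(1 − g × gap/365) − 0.65, where g is the gap-based share of events. That is 1.8–2.3 points at g = 0.5 and 3.5–4.8 at g = 1, for gaps of 45 and 60 days. A reader might add this to the size of the conflict. It should not be added, because it arises even if nobody leaves the VA.

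**Conclusion.** The conflict is real: the gap window omits an end point that the follow-up definition includes, and no censoring rule resolves it. On the reading that the surrounding text favours, it lowers 12-month persistence by about 1 point at most. On the literal reading it costs about 1 to 5 points. Both rest on assumed leaving of 2% to 10% per year, a rate the documents do not give, and on 65% true persistence.

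Only exploratory objectives are affected. The race hazard ratio is essentially unchanged unless leaving differs by race, and a reader who infers a biased race comparison would need evidence of that difference, which the documents do not contain. The point deserves correction before analysis because two competent programmers could code the same patient differently. It does not threaten the study.

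**What to change.** 1. In Table 3, end the gap window at the earliest of next prescription, end of continuous eligibility or end of data.
2. In Sections 9.7.2.3 and 9.7.3, censor at end of follow-up any patient who has not reached the gap threshold by then, and date the gap-based event on the day the threshold is reached. In simulation this pairing stayed within 0.2 points of the true value. Dating at end of supply while counting on-drug time to end of follow-up overstated persistence by 0.1–2.2 points.
3. Keep death and ADT switch as persistence events, as Table 3 has them. Say separately whether death is an event or a censoring point for time to discontinuation, which the plan leaves open.
4. In Section 9.2.1, define end of continuous eligibility independently of relugolix fills.
5. Report the gap-to-end-of-data version as a sensitivity analysis and show the two together as bounds. At 5% leaving with 10% of stoppers lost, they gave 63.1–63.2% and 66.4–67.6% around a true value of about 65%.

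The cost is one phrase in Table 3, two sentences in Sections 9.7.2.3 and 9.7.3, one definition in Section 9.2.1 and one extra Kaplan-Meier run on data already held. The downside is informative censoring if eligibility ends at last recorded activity: persistence could be overstated by about 1 to 6 points when 5% to 20% of stoppers have no later activity. Steps 4 and 5 limit that and make it visible.
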